7.5.2.5	Efficacy for Participants Treated Beyond Progression	28
7.5.3	Subset Analyses	29

7.5.4	Interim Analysis	29
7.6	Safety	29
7.6.1	Deaths	29
7.6.2	Serious Adverse Events	29
7.6.3	Adverse Events Leading to Discontinuation of Study Therapy	29
7.6.4	Adverse Events Leading to Dose Modification	30
7.6.5	Adverse Events	30
7.6.6	Select Adverse Events	30
7.6.7	Immune Modulating Medication	30
7.6.8	Multiple Events	30
7.6.9	Other Events of Special Interest	30
7.6.10	See Core Safety SAP. Immune-Mediated Adverse Events	30
7.6.11	Laboratory Parameters	30
7.6.11.1	Hematology	30
7.6.11.2	Serum Chemistry	30
7.6.11.3	Electrolytes	30
7.6.11.4	Additional Analyses	30
7.6.12	Vital Signs and Pulse Oximetry	30
7.6.13	Immunogenicity Endpoints	31
7.6.14	Pregnancy	31
7.6.15	Adverse Events by Subgroup	31
7.7	Pharmacokinetics	31
7.8.1	PD-L1 Analyses	31
7.8.1.1	Distribution of Baseline PD-L1 expression	32
7.8.1.2	Association between PD-L1 status at baseline and efficacy measures	32
7.8.2	Analyses on 9p24.1 Alterations	32
7.8.3	EBV Status	33
7.9	Outcomes Research Analyses	33
7.9.1	EQ-5D-3L questionnaire	33
7.9.2	EORTC-QLQ-C30	33
7.9.3	EORTC-QLQ-BN-20	34

8	CONVENTIONS.....	35
9	CONTENT OF REPORTS	36
11	DOCUMENT HISTORY.....	36

[REDACTED]

LIST OF TABLES

Table 2.4-1:	Protocol Amendments	8
Table 4.2.1-1:	Censoring scheme used in primary analysis of PFS.....	11
Table 4.3.6-1:	Analysis Time Windows for EQ-5D-3L Assessments for PCNSL.....	14
Table 4.3.6-2:	Analysis Time Windows for EQ-5D-3L Assessments for PTL.....	15
Table 5-1:	Observed ORR with Exact 95 % CI.....	19
Table 7.4.1-1:	Administration of study therapy: definition of parameters.....	24
Table 11-1:	Document History	36

LIST OF FIGURES

Figure 2.1-1:	Study Design.....	7
---------------	-------------------	---

Research Hypothesis:

Treatment with nivolumab will demonstrate clinically meaningful efficacy in subjects with relapsed/refractory PCNSL or PTL.

Schedule of Analyses:

The analysis of the primary endpoint in each cohort will occur at least 6 months after last patient first treatment in each cohort. Secondary endpoints will be analyzed at the same time as the primary endpoint.

2 STUDY DESCRIPTION

2.1 Study Design

[figure not shown]
CA209647 is a Phase 2, open-label, single-arm, 2-cohort study to estimate the safety and efficacy of nivolumab in participants with relapsed/refractory PCNSL or PTL. Nivolumab 240 mg will be given every 2 weeks for 8 cycles. Beginning with Cycle 9, nivolumab 480 mg will be given every 4 weeks for a total therapy duration of 2 years, or until progressive disease, unacceptable toxicity, or withdrawal of consent. Nivolumab will be administered as a 30-minute infusion. A finite treatment duration with immune therapies in this patient population remains an area of ongoing research; therefore the treatment duration chosen was 2 years.

The study will further characterize safety and evaluate the antitumor activity of nivolumab in participants with relapsed/refractory PCNSL or PTL who progressed after or did not respond to at least 1 line of systemic therapy.

The primary endpoint is BICR-assessed ORR, and will be analyzed 6 months after last patient first treatment in each cohort.

This study will consist of 3 phases: screening, treatment, and follow-up. The study design schematic is presented in [Figure 2.1-1](#).

Figure 2.1-1: Study Design

2.2 Treatment Assignment

Participants will be identified and informed consent obtained. Participants must be enrolled into the study by the interactive web response system (IVRS) to obtain the participant number. The investigator or designee will register the participant for enrollment by following the procedures established by BMS.

2.3 Blinding and Unblinding

Not applicable. This is an open-label study.

2.4 Protocol Amendments

Table 2.4-1: Protocol Amendments

Document	Date of Issue	Summary of Change
Revised Protocol 04	29-Nov-2017	To characterize nivolumab pharmacokinetic [REDACTED] in the cerebrospinal fluid (CSF), lumbar puncture(s) (optional) have been added and will be obtained from consenting patients with relapsed/refractory PCNSL or relapsed/refractory PTL with CNS involvement. [REDACTED]
Administrative Letter 06	04-Sep-2017	Corrected the Appendix 6 of the protocol (Tumor Flare; Treatment strategies during TF) by removing the CTCAE classification of cerebral edema.
Revised Protocol 03	07-Apr-2017	Incorporates Amendment(s) 09 Changes to eligibility - To allow enrollment of subjects with PTL who undergo orchiectomy - To allow enrollment of subjects with PTL with measurable nodule disease - To specify more precisely the first line of therapy in PCNSL and PTL - To exclude subjects with significantly increased risk for bleeding complications - To lower the dose of dexamethasone or equivalent allowed 14 days prior to first dose of nivolumab to less than or equal to 2mg/day. The use of CT Scans without PET scans will not be allowed for assessment for subjects with PTL. Added the possibility for administrative interim analyses. Recommendations for the management of Tumor Flare have been added as Appendix 6.
Amendment 09	07-Apr-2017	Incorporates changes per Administrative Letters 04, 03, and 02.
Administrative Letter 04	07-Feb-2017	Change Medical Monitor address.
Administrative Letter 03	17-Nov-2016	To further clarify protocol requirements for tumor tissue submission at screening and correct typographic errors in Table 5.1-2 of the protocol.
Administrative Letter 02	20-Oct-2016	Clarify the protocol requirements for tumor tissue submission at screening.
Revised Protocol 02	05-Oct-2016	Incorporates Amendment(s) 05
Amendment 05	05-Oct-2016	To reflect update in the treatment management algorithms to be consistent with the updated nivolumab investigator brochure (IB) V15, updates to the acceptable methods of contraception in order to be consistent with the most recent version of BMS SOP and IB V15. To allow the enrollment of patients with PCNSL that cannot produce a minimum of 25 slides [REDACTED]

Table 2.4-1: Protocol Amendments

Document	Date of Issue	Summary of Change
		Other changes were made to resolve minor inconsistencies or to provide clarifications.
Revised Protocol 01	22-Jun-2016	
Incorporates Amendment(s) 01
 
Subjects in the cohorts with PCNSL and PTL with brain and or spinal lesions are allowed to enroll if they are on 4 mg per day or less of dexamethasone.
 
Subjects who had undergone allogeneic stem cell transplant > 12 months prior to first dose of study drug, have no evidence of active graft versus host disease, and are not on systemic immunosuppressive therapy are allowed to participate in the study.
 
Neurologic Assessment in Neuro-Oncology (NANO) has been incorporated in the exploratory endpoints in the protocol.

Amendment 01	22-Jun-2016	
If the dose of dexamethasone is increased during the screening period following the screening MRI, and if there is clinical worsening in neurological symptoms following the MRI, the MRI must be repeated.
 
Due to the rapidly progressing nature of CNS tumors, a brain MRI is to be performed within 14 days before the first dose of study treatment in both cohorts in order to accurately reflect the disease burden.
 
Language was added for the collection of prospective blood samples, and for BMS to retain residual blood and tissue samples, so that scientists can perform additional research.
 
Incorporation of other minor changes to correct and/or clarify protocol requirements.

2.5 Data Monitoring Committee

Not applicable.

3 OBJECTIVES

3.1 Primary Objective

To assess the clinical benefit of nivolumab in subjects with relapsed/refractory PCNSL or relapsed/refractory PTL as measured by ORR by blinded Independent Central Review (BICR).

3.2 Secondary Objectives

- To assess progression free survival (PFS) based on BICR assessment for PCNSL or PTL, respectively

- To assess ORR and duration of response (DOR) based on investigator assessment for PCNSL or PTL, respectively
- To assess overall survival (OS) for PCNSL or PTL, respectively

4 ENDPOINTS

4.1 Primary Endpoint(s)

The primary objective will be measured by the primary endpoint of BICR-assessed ORR. It is defined as the number of participants with a best overall response (BOR) of CR, unconfirmed complete response (CRu) or PR, based on the IPCG Criteria for PCNSL and Lugano 2014 response evaluation for PTL, divided by the number of treated participants within each cohort.

The BICR-assessed BOR is defined as the best response designation recorded between the date of first study drug dose and the date of initial objectively documented progression per criteria or the date of subsequent therapy, whichever occurs first. For purposes of analysis, if a participant receives one dose and discontinues the study without assessment or receives subsequent therapy prior to assessment, this participant will be counted in the denominator (as non-responder).

The BICR-assessed objective response will be further characterized by the time to response (TTR) and duration of response (DOR).

TTR is defined as the time from first dosing date to the date of the first response, based on BICR assessment. TTR will be evaluated for responders only.

DOR is defined as the time from first response (CR, CRu or PR) to the date of initial objectively documented progression as determined using the IPCG Criteria for PCNSL and Lugano 2014 response evaluation for PTL, as determined by BICR, or death due to any cause, whichever occurs first. For participants who neither progress nor die, the DOR will be censored on the date of their last tumor assessment. Participants who start subsequent anticancer therapy without a prior reported progression will be censored at the last tumor assessments prior or on the first subsequent anticancer therapy date. The censoring scheme of DOR will be the same as the primary censoring scheme for PFS. This endpoint will only be evaluated in participants with objective response of CR, CRu or PR.

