Study sites will retain local access to the imaging results for safety and efficacy reading purposes. The study investigator will review the local FDG PET-CT results as clinically appropriate to ensure that any potentially emergent clinical situations are addressed in a timely fashion. Clinically significant radiologic findings or changes from baseline scans will be coded as AEs or SAEs according to the criteria described below in [Section 6](#).

At baseline, for staging purposes all PTL subjects will undergo the following procedures:

- FDG PET/CT scan
- Gadolinium-enhanced MRI of the brain
- Gadolinium-enhanced MRI of the spine (in subjects with spinal symptoms)
- Bone marrow biopsy with aspirate, if clinically indicated
- Lumbar puncture for CSF cytology, if clinically indicated
- Eye examination for PTL patients with CNS involvement

If brain and/or spine MRI, bone marrow biopsy, or CSF cytology are positive for lymphoma involvement at baseline, these tests must be repeated for confirmation of objective response.

On-study Assessment of Response

PCNSL

Assessment of treatment response in subjects with PCNSL while on study requires the following assessments:

- Gadolinium-enhanced MRI scan of the brain
- Gadolinium-enhanced MRI scan of the spine, if positive at baseline or if clinically indicated
- Detailed ophthalmological examination with dilated fundus examination, slit-lamp examination, and color photography of the posterior pole, if clinically indicated and for confirmation of objective response
- Whole-body CT scan, if clinically indicated
- Lumbar puncture for CSF cytology, if clinically indicated
- Bone marrow biopsy with aspirate, if clinically indicated

The criteria for response assessment are illustrated in [Appendix 3](#). Additionally, objective response requires confirmation by repeat brain MRI at 8 weeks from the initially documented response. If MRI of the spine, ophthalmological examination, CSF cytology, or bone marrow biopsy are positive for lymphoma involvement at baseline or on-study when warranted by symptoms, these tests should be also repeated at 8 weeks for confirmation of objective response.

PTL

Assessment of treatment response in subjects with PTL while on study requires the following assessments:

- FDG PET-CT scan
- Bone marrow biopsy with aspirate, if clinically indicated
- Gadolinium-enhanced MRI scan of the brain and/or of the spine, if clinically indicated
- Lumbar puncture for CSF cytology, if clinically indicated

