- Eye examination for PTL patients with CNS involvement

The criteria for response evaluation in PTL patients are described in [Appendix 4](#). Additionally, objective response requires confirmation by repeat brain MRI at 8 weeks from the initially documented response (only for patients with CNS involvement per IPCG criteria). If bone marrow biopsy, brain and/or spine MRI, or CSF cytology are positive for lymphoma involvement at baseline or on-study when warranted by symptoms, these tests should be also repeated at 8 weeks for confirmation of objective response.

Radiographic Assessments

Radiographic study evaluations will take place as outlined in [Section 5.1](#).

Baseline assessments should be performed within 28 days prior to the first dose (14 days for MRI of the brain). A whole-body PET/CT is required at baseline for all subjects.

On-study assessments should include chest, abdomen, and pelvis, and all known sites of disease (including CNS and/or spine) and should use the same imaging method that was used at baseline.

PCNSL subjects will be evaluated for tumor response by MRI at Week 8 from the first dose and continuing for every 8 weeks for the first 2 years (104 weeks). PTL subjects will be evaluated for tumor response by FDG-PET/CT or PET/MRI at Week 8 from the first dose and continuing for every 8 weeks for the first 6 months (26 weeks), then every 12 weeks for 18 months. After the first 2 years, tumor assessments are to occur every 24 weeks until disease progression is documented.

Assessment of Overall Tumor Burden and Measurable Disease

To serially evaluate tumor response to therapy, it is necessary to estimate the overall tumor burden at baseline and use this as a comparator for subsequent measurements. Measurable disease is defined by the presence of at least one measurable tumor lesion. At baseline, tumor lesions/lymph nodes will be categorized as measurable or non-measurable.

Measurable Lesions

- Focal uptake in nodal and extranodal sites that is in keeping with lymphoma, according to the distribution and/or CT characteristics, is considered involvement with lymphoma, including spleen, liver, bone, thyroid, and so on.
- Measured dominant lesions: Up to 6 of the largest dominant nodes, nodal masses, and extranodal lesions selected to be clearly measurable in 2 diameters.

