Any disease not selected as measured, dominant disease and truly assessable disease should be considered not measured. These sites include any nodes, nodal masses, and extranodal sites not selected as dominant or measurable or that do not meet the requirements for measurability but are still considered abnormal, as well as truly assessable disease, which is any site of suspected disease that would be difficult to follow quantitatively with measurement, including pleural effusions, ascites, bone lesions, leptomeningeal disease, abdominal masses, and other lesions that cannot be confirmed and followed by imaging. In Waldeyer's ring or in extranodal sites (eg, GI tract, liver, bone marrow), FDG uptake may be greater than in the mediastinum with complete metabolic response, but should be no higher than surrounding normal physiologic uptake (eg, with marrow activation as a result of chemotherapy or myeloid growth factors).

All other lesions (or sites of disease) including non-measurable lymph nodes should be identified as non-target lesions and should also be recorded at baseline. Measurements are not required and these lesions should be followed as 'present', 'absent', or in rare cases 'unequivocal progression'. In addition, it is possible to record multiple non-target lesions involving the same organ as a single item on the CRF (eg, 'multiple enlarged pelvic lymph nodes' or multiple liver nodules').

Bone Marrow Assessments

Bone marrow assessments should be done only if clinically indicated in both subjects with PCNSL or PTL. The biopsy/aspirate performed within 90 days prior to obtaining informed consent must be documented at screening or a bone marrow biopsy/aspirate must be performed during the screening period if clinically indicated. For PCNSL or PTL subjects with bone marrow involvement at screening, a bone marrow biopsy and aspirate will be required to confirm an objective response.

In addition to efficacy assessments, additional, optional, bone marrow biopsy and aspirate samples may be collected and submitted for biomarker studies.

CSF Assessments

CSF cytology should be done if clinically indicated. If performed within 90 days prior to obtaining informed consent they must be documented at screening or a lumbar puncture must be performed during the screening period. For PCNSL or PTL subjects with CSF involvement at screening, a lumbar puncture with CSF collection will be required to confirm an objective response.

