8.3 Endpoints

8.3.1 Primary Endpoint(s)

The primary objective will be measured by the primary endpoint of BICR-assessed ORR. It is defined as the number of subjects with a best overall response (BOR) of CR or PR, based on the IPCG Criteria for PCNSL²¹ and Lugano 2014 response evaluation for PTL,²² divided by the number of treated subjects within each cohort.

The BICR-assessed BOR is defined as the best response designation recorded between the date of first study drug dose and the date of initial objectively documented progression per criteria or the date of subsequent therapy, whichever occurs first. For purposes of analysis, if a subject receives one dose and discontinues the study without assessment or receives subsequent therapy prior to assessment, this subject will be counted in the denominator (as non-responder).

The BICR-assessed objective response will be further characterized by the DOR, defined as the time from first response (CR or PR) to the date of initial objectively documented progression as determined using the IPCG Criteria for PCNSL and Lugano 2014 response evaluation for PTL, as determined by BICR, or death due to any cause, whichever occurs first. For subjects who neither progress nor die, the DOR will be censored on the date of their last tumor assessment. Subjects who start subsequent anticancer therapy without a prior reported progression will be censored at the last tumor assessments prior to initiation of the subsequent anticancer therapy. This endpoint will only be evaluated in subjects with objective response of CR or PR.

The analysis of the primary endpoint in each cohort will occur at least 6 months after last patient first treatment in each cohort.

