APPENDIX 3 RESPONSE CRITERIA FOR PCNSL

Subjects with PCNSL will be evaluated using the International Primary CNS Lymphoma Collaborative Group (IPCG) Criteria for PCNSL¹⁴.

Table 1: Response criteria for PCNSL				
Response	Criteria			
	Brain imaging	Corticosteroid dose	Eye examination	CSF cytology
Complete response (CR)	No contrast enhancement	None	Normal	Negative
Unconfirmed complete response (CRu)	No contrast enhancement	Any	Normal	Negative
	Minimal abnormality	Any	Minor RPE abnormality	Negative
Partial response (PR)	50% decrease in enhancing tumor	Irrelevant	Minor RPE abnormality or normal	Negative
	No contrast enhancement	Irrelevant	Decrease in vitreous cells or retinal infiltrate	Persistent or suspicious
Progressive disease (PD)	25% increase in lesion	Irrelevant	Recurrent or new ocular disease	Recurrent or positive
	Any new site of disease: CNS or systemic			

Source: Abrey et al., 2005

Complete Response (CR):

- Complete disappearance of all enhancing abnormalities on gadolinium-enhanced MRI.
- No evidence of active ocular lymphoma as defined by absence of cells in the vitreous and resolution of any previously documented retinal or optic nerve infiltrates. Chronic changes of the retinal pigment epithelium in the setting of a prior retinal or optic nerve infiltrate does not preclude the definition of a CR. Detailed ophthalmologic examination with dilated fundus examination, slit-lamp examination and color photography of the posterior pole, and lumbar puncture for cytology are required only if these studies were initially positive or became positive during treatment and if clinically indicated by new symptoms or signs.
- Lumbar puncture for CSF cytology is necessary to confirm cytologic response observed in the ventricular CSF.
- At the time a CR is determined, the patient should have discontinued corticosteroids for at least 2 weeks.
- Residual lesions (other than lesions < 10 mm) if presumed to be non-malignant should be further investigated (eg, by PET scans) before CR can be accepted.
- If there was evidence of PET abnormality suspicious for systemic disease then PET has to be repeated to confirm CR (Radiology comment)

- All subjects who appear to achieve CR require the following:
 - Confirmation scan at 8 weeks
 - Repeat CSF cytology, bone marrow biopsy and aspirate, and ophthalmologic examination if involved at baseline

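### Protocol 5.4.1 requires 8-week confirmation of objective response, but the primary BOR rule has no confirmation step, so read literally a single-scan PR counts towards primary ORR

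*SAP*

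**What the plan says.** Protocol 5.4.1 (On-study Assessment of Response, PCNSL) refers to Appendix 3 for the response criteria and then adds a condition: "Additionally, objective response requires confirmation by repeat brain MRI at 8 weeks from the initially documented response". For PTL the same condition applies with a restriction: "from the initially documented response (only for patients with CNS involvement per IPCG criteria". Section 5.4.1 also asks for certain tests to be repeated. In PTL the trigger is worded "If bone marrow biopsy, brain and/or spine MRI, or CSF cytology are positive for lymphoma involvement at baseline or on-study when warranted by symptoms", and the Bone Marrow Assessments paragraph says that for "PTL subjects with bone marrow involvement at screening, a bone marrow biopsy and aspirate will be required to confirm an objective response".

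The primary endpoint rule is worded differently. Protocol 8.3.1 and SAP 4.1 share the same definition: "BOR is defined as the best response designation recorded between the date of first study drug dose" and progression or subsequent therapy. Neither refers to 5.4.1, gives a confirmation window, or says what an unconfirmed response becomes. SAP 7.5.1 lists the BOR categories as CR, CRu, PR, SD, PD, non-evaluable and not reported, with no split by confirmation.

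Appendix 3 falls between the two. Under CR it says "All subjects who appear to achieve CR require the following" and then names an 8-week confirmation scan. Its PR list, presented as complete, contains no repeat scan.

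**The concern.** Both documents define the primary endpoint by reference to the IPCG and Lugano criteria. For PR in PCNSL, the criteria as set out in Appendix 3 are met on one scan. Section 5.4.1 says that is not enough. Two analysts working from the same scans, one applying 5.4.1 and the other SAP 4.1, would report different primary ORRs whenever a PR is not reproduced 8 weeks later.

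The discrepancy runs one way. The denominator is all treated subjects under either rule, and confirmed responders are a subset of those with any recorded response. The same responder set feeds time to response and duration of response, and investigator-assessed ORR and DOR are defined in the same way.

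**Working it through.** **1. The texts side by side, for one PCNSL patient.** PR at the Week 8 MRI, PD at the Week 16 MRI.

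- Protocol 8.3.1 and SAP 4.1: the best designation before progression is PR, so the patient is a responder.
- Protocol 5.4.1: the repeat MRI 8 weeks after the first PR shows progression, so there is no confirmed objective response.
- DOR under the literal rule, using the SAP section 8 formula (last date − first date + 1): 56 + 1 = 57 days; 57/30.4375 = 1.87 months. Under a confirmed rule the patient does not enter DOR at all.

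**2. The plan's own figures.** Inputs: N = 45 and N = 20, benchmark 14%, two-sided 95% Clopper-Pearson limits (SAP sections 5 and 7.5.1). The lower limit for x responders out of n is the 2.5% quantile of Beta(x, n − x + 1). All nine intervals in SAP Table 5-1 reproduce; for example, 13/45 gives 16.4% to 44.3% and 8/20 gives 19.1% to 63.9%.

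**3. Removing responders.**

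| Cohort | Responders | ORR | Lower limit | Excludes 14%? |
|---|---|---|---|---|
| PCNSL | 18/45 | 40.0% | 25.7% | yes |
| PCNSL | 13/45 | 28.9% | 16.4% | yes |
| PCNSL | 12/45 | 26.7% | 14.6% | yes |
| PCNSL | 11/45 | 24.4% | 12.9% | no |
| PTL | 8/20 | 40.0% | 19.1% | yes |
| PTL | 7/20 | 35.0% | 15.4% | yes |
| PTL | 6/20 | 30.0% | 11.9% | no |

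From the planning results, two losses are needed in either cohort (13 − 11 = 2; 8 − 6 = 2). From 18/45, seven are needed (18 − 11 = 7). In PTL a loss under the MRI rule can come only from a patient with CNS involvement, and the documents do not say how many there will be.

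**4. Why no probability is attached.** The chance of losing at least two of 13 responders depends on two unknowns. With assumed independent non-confirmation rates of 10%, 20% and 30%, it is 38%, 77% and 94% if all 13 are exposed. CR already carries the 8-week scan in Appendix 3, however. If only 7 of the 13 were PR (also an assumption), the figures are 15%, 42% and 67%. For 7 responders at 10%: 1 − 0.9^7 − 7 × 0.1 × 0.9^6 = 0.150.

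**5. Timing.** The primary analysis may take place 6 months after the last first dose: 6 × 30.4375/7 = 26.1 weeks. On the 8-weekly schedule, first responses at Weeks 8 and 16 can be confirmed at Weeks 16 and 24. A first response at Week 24 needs a scan near Week 32, after the minimum cut-off.

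**The case against.** The strongest reply is that this is silence, not conflict. Section 8.3.1 belongs to the same protocol as 5.4.1, and both 8.3.1 and SAP 4.1 use the term objective response. One can read them as meaning that CR or PR is recorded only once 5.4.1 is satisfied. Protocol section 7 also leaves the process of the independent read to the Imaging Review Charter, which may apply confirmation before any designation is recorded. Some of the schedule tables in section 5.1 are redacted or not visible. These points stand to this extent: the documents do not show how the central reviewers will in fact read the scans. They do not remove the gap. Neither endpoint definition cites 5.4.1 or the charter as the analysis rule, and importing 5.4.1 by implication would still supply no window and no rule for a missed or pending scan.

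A second reply is that the CRu category deals with unconfirmed responses. It does not. In Appendix 3, CRu concerns continued steroid use or minor eye findings rather than a missing repeat scan, and SAP 4.1 counts it as a response.

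A third reply is that 14% is not a decision threshold. That is correct. The study is estimative, the PCNSL size was set empirically for safety, and there is no formal test against 14%.

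**Conclusion.** The point holds. The protocol's assessment section and the primary endpoint rule in both documents disagree on whether a PR must be confirmed. Read literally, a single-scan PR in PCNSL, or in CNS disease in PTL, enters primary ORR, TTR and DOR although 5.4.1 does not accept it. This rests on the literal text and on the charter not already applying confirmation.

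The effect on ORR is upward or nil. Its size cannot be stated from the documents. The two-responder illustration applies near the planning results; at 18/45 or above the comparison with 14% is much less sensitive.

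Three stronger readings are tempting and not supported:

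- A reader might infer that the reported ORR will be inflated. That requires both that some responses fail confirmation and that the central review records unconfirmed designations. Neither is shown.
- A reader might infer that the exclusion of 14% would probably be lost at 13/45. That treats every responder as exposed and assumes a non-confirmation rate that is not given. It also treats a descriptive benchmark as a test.
- A reader might infer that every PTL response needs an 8-week repeat. The MRI condition covers only CNS involvement, and a Lugano response in systemic-only disease on one PET-CT does not contradict it. Marrow repeats are a separate requirement and can apply without CNS disease.

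**What to change.** Reconcile SAP 4.1 and 7.5.1, protocol 8.3.1 and Appendix 3 with protocol 5.4.1. Since 5.4.1 is the stated requirement, the natural choice is:

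- make confirmed response (CR and PR) the primary BOR for PCNSL and for CNS disease in PTL, with a stated window around 8 weeks;
- name the BOR class given to a failed, missed or pending-at-cut-off confirmation;
- date the response at its first documentation for TTR and DOR;
- state what result of a repeated CSF, eye or marrow test counts as confirming, consistently with Appendix 3, which allows PR with persistent malignant cells in CSF or eye;
- leave Lugano systemic imaging responses outside the MRI rule;
- report ORR without confirmation as a sensitivity analysis.

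If the sponsor prefers to keep the unconfirmed rule as primary, amend 5.4.1 and report confirmed ORR as the sensitivity analysis. Either way the charter should say the same thing.

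The cost is wording and an extra table. The confirmatory assessments are already required by 5.4.1, and PCNSL MRI is 8-weekly for 2 years. There are two real costs. First, the pending rule can itself change ORR, because a first response at Week 24 is unconfirmed at the minimum cut-off. Second, some first responses have no scheduled 8-week scan (PTL imaging becomes 12-weekly after 6 months, and follow-up imaging after treatment is 6-monthly), so the missed-confirmation rule must cover them. Investigator-assessed endpoints and the subset analyses in SAP 7.5.3 need the same definition.

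Separately, the responder categories differ: protocol 8.3.1 has "It is defined as the number of subjects with a best overall response (BOR) of CR or PR", while SAP 4.1 has "best overall response (BOR) of CR, unconfirmed complete response (CRu) or PR". That should be resolved as its own point.
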